5.2. Study Rationale

The initial proposed indication for ACE-083 is facioscapulohumeral muscular dystrophy (FSHD), which is the third most common muscular dystrophy and has an autosomal dominant pattern of inheritance in most patients compared to a less common sporadic form which affects approximately 10-30% of patients.^{6,7} FSHD has a prevalence of 1:15,000-1:20,000.^{6,7} FSHD is characterized by complex genetic mechanisms relating to the double homeobox protein 4 gene (DUX4). DUX4 is normally repressed through epigenetic mechanisms in somatic cells and is derepressed in FSHD leading to toxic damage to skeletal muscle cells. The DUX4 gene is located in the D4Z4 microsatellite array in the 4q35 region. In FSHD1, one D4Z4 allele is contracted (1 to 10 repeat units) and has been associated with DNA hypomethylation and chromatin structural changes. FSHD2 accounts for about 5% of FSHD cases and has been characterized by hypomethylation of both normal D4Z4 alleles. Mutations in the SMCHD1 gene resulting in changes in the D4Z4 chromatin structure have been linked to FSHD2. Both types are phenotypically indistinguishable.⁸ Other rare atypical variants of the disease can also manifest in the setting of a genetic diagnosis.

FSHD patients typically present in their second decade of life and live a normal lifespan. The disease is clinically characterized by slowly progressive focal asymmetric areas of muscle weakness involving the facial, scapular, upper arm, lower leg, and abdominal muscles. Biceps and triceps involvement can affect upper arm flexion and extension limiting ability to lift objects and perform activities of daily living. Weakness of the tibialis anterior (TA), a commonly affected lower extremity muscle in FSHD patients, often results in impaired dorsiflexion and foot drop. Foot drop can lead to gait instability and falls requiring the use of braces, walking devices, and wheelchairs. About 20% of FSHD patients become non-ambulatory. Other clinical complications associated with FSHD may involve respiratory muscle weakness, resulting in pulmonary complications, retinovascular disease, chronic pain, and hearing loss.⁹ Laboratory and muscle biopsy findings are often non-specific and therefore are not required for diagnosis. Elevations in creatine kinase (CK) can be seen but are often normal in asymptomatic patients. Muscle biopsy can show variable changes in muscle fiber size (both hypertrophy and atrophy) and inflammatory cellular infiltrates.¹⁰

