^a Injection into muscle once every three weeks^b Dose level for Cohorts 2 and 3 to be determined by SRT, not to exceed 250 mg per muscle**Part 2: N=Up to 56^a (6-month, randomized, double-blind, placebo-controlled and 6-month open-label extension)**

6-month, double-blind, placebo-controlled			
Muscle	Dose Level ^b	ACE-083 n	Placebo n
Tibialis anterior	TBD ^c	14	14
Biceps brachii	TBD ^c	14	14

6-month open-label extension		
Muscle	Dose Level ^b	ACE-083 n
Tibialis anterior	TBD ^c	28
Biceps brachii	TBD ^c	28

^a N=14 active, 14 placebo per muscle.^b Injection into muscle once every three weeks^c Based on review of Part 1, not to exceed 250 mg per muscle**10.1.1. Individual Dose Modification Rules**

For an adverse event (AE, including injection site reactions) of Grade 3 or higher, regardless of relationship to study drug, treatment will be paused and the patient will be monitored weekly. Dosing may resume upon resolution of the AE to \leq Grade 1 or baseline, and dose level may be reduced to the prior dose level deemed safe by SRT, at the discretion of the investigator. Dose level should be reduced by one level (i.e., from 240 to 200 mg or from 200 to 150 mg) for events related to study drug for the remainder of the study; treatment will be discontinued if event occurred at 150 mg dose. If dosing does not resume within 6 weeks of the last dose given, the patient will be discontinued from treatment.

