13. SAFETY

13.1. Definition of Adverse Events

13.1.1. Adverse Event

For this protocol, an adverse event (AE) is any untoward medical occurrence in a clinical investigational study where a patient is administered a study drug (i.e., on or after the Cycle 1 Day 1 dose), which does not necessarily have a causal relationship with this treatment. An AE can therefore be any unfavorable and unintended sign (including an abnormal laboratory finding), symptom, or disease temporally associated with the use of the study drug whether or not it is considered related to the study drug.

Abnormal laboratory and other abnormal investigational findings (e.g., physical exam, ECG) should not be reported as AEs unless they are associated with clinical signs and symptoms, lead to treatment discontinuation, or are otherwise considered clinically relevant by the investigator. In cases of surgical or diagnostic procedures, the condition/illness leading to such a procedure is considered as the AE rather than the procedure itself. In the case of a fatality, the cause of death is considered as the AE, and the death is considered as its outcome.

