### 4.1.5. Data Handling Conventions

Unless otherwise stated or indicated:

- Individual data for all patients will be presented in data listings, sorted by “Study Part” (Part 1 or Part 2), “Treatment Group”, and “Patient Number”;
- For any parameter analyzed, only observations from visits and/or time points planned in the protocol will be used in descriptive statistics. An exception to this rule is for a baseline assessment. Should an unscheduled assessment be taken after the scheduled baseline assessment but before the first dose of study medication, then the unscheduled assessment may be used as the baseline;
- For variables where the Day 1 assessment is defined as the baseline, should an individual patient have a Day 1 assessment after having received their first dose, then an unscheduled assessment may be used as the baseline, provided that the unscheduled assessment was done prior to first dose.
- For variables where the baseline is defined as the mean of Day -28, Day -7, and Day 1, should an individual patient have a Day 1 assessment taken after having received their first dose, then only the Day -28, Day -7, and any unscheduled assessment will be used to determine the average for the baseline (as described in [Section 4.1.4](#)), provided that the unscheduled assessment was done prior to first dose.
- For the determination of baseline PUL, only data on the patient’s preferred side will be used. For example, if the patient’s preferred side is “Left” and any individual PUL assessment at any of the Day -28, Day -7, and Day 1 timepoints is recorded as having been done on the “Right” or performed as “Both”, that individual assessment will not be used in the determination of the baseline PUL for that patient.
- With the exception of what is described in the preceding bullet, unscheduled assessments will not be collectively summarized in summary tables or figures; however, these data will appear in individual patient listings.
- For adverse events where the assessment of “Relationship to study drug” is missing, it will be assumed that the adverse event is “Probably Related” to study drug.
- For selected efficacy data, tests of statistical hypotheses and estimation using the end-of-treatment visit or the Day 190 visit (Part 2 double-blind component), multiple imputation for missing data will be performed. There will be no imputations performed for patients who discontinued prior to Day 43 and were replaced.

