#### 4.9.2. Clinical Laboratory Evaluations

The following table lists the planned clinical laboratory assessments:

Type of Assessment	Details
Hematology	Hemoglobin, hematocrit, platelet count, red blood cell count, white blood cell (WBC) count, and WBC differential
Chemistry	AST, ALT, lactate dehydrogenase (LDH) and isoenzymes 1-5, gamma-glutamyl transpeptidase (GGT), blood urea nitrogen (BUN), creatinine, creatine kinase (CK), myoglobin, aldolase, sodium, potassium, glucose, albumin, total bilirubin
Urine	Urinalysis by dipstick analysis (pH, specific gravity, protein, myoglobin, glucose, ketones, blood, leukocyte esterase, and nitrite)

In addition to the tests listed below, a urine pregnancy test is performed on all females of childbearing potential according to scheduled times listed in the protocol.

Descriptive statistics of raw data and change from baseline data will be provided by treatment group for each scheduled time.

Plots of individual patient data will be provided by treatment group and scheduled time for continuous laboratory data. Plots of mean  $\pm$  SEM will be provided for raw data and change from baseline data for the following selected laboratory data: hemoglobin, glucose, aldolase, blood urea nitrogen (BUN), creatinine kinase (CK), creatinine, and myoglobin.

Shift tables describing out-of-range shifts from baseline (in frequency counts) will be created for post-dose time points.

Additional analyses may be performed as appropriate.

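### No laboratory table counts patients by worst post-baseline grade, and unscheduled laboratory values stay out of every table and figure

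*SAP*

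**What the plan says.** SAP 4.1.5 (Data Handling Conventions) says, for any parameter analysed, that "only observations from visits and/or time points planned in the protocol will be used in descriptive statistics". The stated exception concerns the choice of a baseline value before the first dose. A later bullet extends the rule from descriptive statistics to every table and figure: "unscheduled assessments will not be collectively summarized in summary tables or figures; however, these data will appear in individual patient listings". Safety data are not exempted.

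SAP 4.9.2 (Clinical Laboratory Evaluations) plans four outputs:

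- "Descriptive statistics of raw data and change from baseline data will be provided by treatment group for each scheduled time". Under SAP 4.1.5 these statistics include the minimum and maximum.
- Plots of each patient's continuous laboratory values by scheduled time.
- Mean plots for seven named tests. CK, creatinine, aldolase and myoglobin are among them; AST and ALT are not.
- "Shift tables describing out-of-range shifts from baseline (in frequency counts) will be created for post-dose time points". No grade, multiple of the upper limit of normal (ULN), multiple of baseline or worst post-baseline value is mentioned.

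The protocol bears on this in four places:

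- Section 5.2 says of FSHD that "Elevations in creatine kinase (CK) can be seen". Section 8.2 sets no CK limit and excludes AST or ALT only from 3 times ULN upward.
- Section 13.1.1 says abnormal laboratory findings "should not be reported as AEs unless they are associated with clinical signs and symptoms", cause treatment to be stopped, or are otherwise clinically relevant in the investigator's view. Section 13.4 requires clinically relevant laboratory changes to be recorded as adverse events.
- Section 10.1.1 says that after an adverse event of Grade 3 or higher, "treatment will be paused and the patient will be monitored weekly".
- Section 14.2.4 promises a summary of toxicity by CTCAE v4.03 grade.

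**The concern.** Safety is the primary objective of Part 1 and a secondary objective of Part 2. The question a reader will bring to the muscle and liver enzymes of an intramuscular drug is how many patients in each group had a marked rise, and from what starting point. The plan has no table that answers it.

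The only table that counts patients classifies values against the normal range. That is least informative where the baseline is already raised, which the protocol's own text makes foreseeable for CK and permits for AST and ALT. Separately, values taken off schedule are often taken because something prompted a closer look, and these are the ones that SAP 4.1.5 removes from tables and figures.

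**Working it through.** The plan gives no figure for this point, so there is none to reproduce. The check has two parts: trace where a laboratory rise would appear, then test the planned outputs on a small example.

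**Tracing a rise through the planned outputs**

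| Rise | Shift table | Change-from-baseline statistics and individual plot | Graded AE tables (SAP 4.9.1) | Listing |
|---|---|---|---|---|
| Planned visit, normal baseline | counted | yes | if recorded as an AE | yes |
| Planned visit, baseline already high | no change of cell | yes, as an extreme value | if recorded as an AE | yes |
| Unscheduled visit, recorded as an AE | no | no | yes | yes |
| Unscheduled visit, not recorded as an AE | no | no | no | yes |

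The second and fourth rows are the gap.

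**Worked example (all values assumed, none from the documents)**

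Take 14 patients, the size of one Part 2 arm in one muscle, and ULN = 200. Baselines are 150, 180, 220, 260, 300, 400, 190, 170, 240, 350, 120, 160, 210 and 280, which sum to 3230. Eight exceed 200. Every patient rises by 5%, except that in one scenario the patient at 400 (400/200 = 2 times ULN) reaches 2400 (2400/200 = 12 times ULN).

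- Without the marked rise, that patient goes from 400 to 420, a change of +20, the largest in the group. The mean change is 0.05 × 3230 / 14 = 161.5 / 14 = 11.5.
- With the rise at a planned visit, the change is 2400 − 400 = +2000. The mean change is (161.5 − 20 + 2000) / 14 = 2141.5 / 14 = 153.0.
- With the rise at an unscheduled visit and 420 at the planned visit, every tabulated figure is as if there had been no rise.

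| Output | No marked rise | Rise at planned visit | Rise at unscheduled visit |
|---|---|---|---|
| High to high | 8 | 8 | 8 |
| Normal to normal | 6 | 6 | 6 |
| Maximum change | +20 | +2000 | +20 |
| Mean change | 11.5 | 153.0 | 11.5 |
| Visible on individual plot | – | yes | no |

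The shift table is the same in all three columns. The continuous summaries detect the rise at a planned visit. They do not say that one patient out of 14 had it, or that it began at 2 times ULN.

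**Timing of planned samples**

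In Part 1 (Protocol Table 5), chemistry after the first dose is planned on Days 22, 43, 64, 85 and 106, with dosing on Days 1, 22, 43, 64 and 85 and samples taken before dosing. Each planned value therefore falls about 21 days after the previous injection (22 − 1, 43 − 22, and so on to 106 − 85). Any chemistry drawn sooner after an injection is off schedule and goes to listings only.

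**The case against.** The best reply is that the plan already has several routes by which a marked rise becomes visible, and most of that reply stands.

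- A reader might infer that laboratory safety is summarised by normal-range shifts alone. It is not. Raw and change-from-baseline statistics with the maximum are planned by treatment group, with individual plots and a mean plot for CK. A rise from a raised baseline at a planned visit does appear in a summary.
- A reader might infer that a rise found during weekly monitoring appears in no summary. The documents do not support that either. Weekly monitoring starts from an adverse event of Grade 3 or higher. If a laboratory rise is the trigger, it is already a graded event, and the adverse event tables are not limited to planned visits. The protocol also names no laboratory panel for the weekly visits, so sampling at them is an inference.
- Protocol 13.4 obliges the investigator to record clinically relevant laboratory changes. For a marked rise to be lost from the tables, it must be both off schedule and judged not relevant.
- The Safety Review Team looks at laboratory results directly when assessing dose-limiting toxicity (Protocol 10.2), so that decision does not depend on the SAP tables.
- The grade summary promised in Protocol 14.2.4 follows the adverse event sentences and can be read as met by the adverse event tables by grade.
- With 14 patients per arm, listings can be read by eye, and SAP 4.9.2 allows additional analyses.

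These points narrow the concern but do not close it. A maximum at each visit is not a count of patients by group. Whether a rise reaches the adverse event tables can rest on an investigator's judgement of relevance. Listings, and analyses that are merely allowed, are not a prespecified comparison.

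**Conclusion.** The point holds in a limited form. SAP 4.1.5 keeps unscheduled laboratory values out of all tables and figures, with no safety exemption, and the only categorical laboratory table is a normal-range shift. Two consequences follow. A rise from an already raised baseline at a planned visit is shown only as an extreme value, not as a counted patient. A marked rise at an unscheduled visit that is not recorded as an adverse event is found only in listings.

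The number of patients affected cannot be given. The documents state neither how often baseline CK, AST or ALT is raised nor how many off-schedule laboratory samples to expect. The example shows how the outputs behave, not how often the situation will occur. The conclusion rests on reading the out-of-range shift as a shift against the normal range, which is its ordinary meaning and the only one that SAP 4.9.2 suggests. The change is worth making because it serves a stated safety objective at little cost. It does not imply that the plan would conceal a safety signal in general.

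**What to change.** In SAP 4.1.5, exempt safety laboratory data from the planned-visit rule for worst-value summaries. By-visit descriptive statistics can stay on planned visits, where mixing in off-schedule values would distort the means.

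In SAP 4.9.2, add a shift table of baseline CTCAE v4.03 grade against worst post-baseline grade:

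- use scheduled and unscheduled values;
- present it by treatment group and muscle (by dose cohort in Part 1);
- cover the gradable analytes, at least CK, AST, ALT and creatinine;
- in Part 2, build it separately for the double-blind and open-label periods, stating the baseline for each and ending the double-blind window before the first open-label dose.

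A patient sampled more often has more chances to record a high worst value, so a footnote giving the number of patients with unscheduled samples in each group would help the reader.

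The cost is a few lines of SAP text and a small amount of programming. The recorded values are already destined for the listings, and no assessment, visit or clinical rule changes.

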14.2.3. Efficacy Data

14.2.3.1. Part 1

MRI

MRI variables will include total muscle volume (TMV) [mm³], intramuscular fat fraction (FF) [%] and other calculated volume and mass parameters.

Muscle strength

- (For TA muscle): Ankle dorsiflexion peak force value which is the maximum of three measurements from the hand-held dynamometer or fixed system,
- (For BB muscle): Elbow flexion peak force value which is the maximum of three measurements from the hand-held dynamometer or fixed system

For each parameter in unilateral cohorts, the raw data as well as the absolute and percent change from baseline in the treated TA or BB muscle, untreated TA or BB muscle, and the treated minus untreated TA or BB muscle will be summarized for each scheduled time point. For dose cohorts where the administration is bilateral, descriptive statistics of raw data, absolute and percent change from baseline will be provided by side treated [right and left] as well as the mean of the right and left sides for MRI and muscle strength parameters.

Baseline is defined as the last non-missing value prior to first dose of ACE-083. Theoretically, this should be the Day 1 pre-dose value. Such summaries will also be done for raw data and change from baseline for each primary efficacy parameter.

Estimates of the effect of ACE-083 on each efficacy parameter and corresponding 90% confidence intervals will be produced for the percent change data described above. For muscle strength parameters, the percent change from the screening to the baseline value will serve as the control for each cohort.

Additional analyses may be performed as appropriate.

14.2.3.2. Part 2

Primary

The primary efficacy endpoint is the percent change in total muscle volume three weeks post last dose of the double-blind treatment period from baseline, where baseline is defined as the last non-missing value prior to first dose of study drug.

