Strength (QMT – by handheld device) ¹²	X	X	X	X	X	X	X	X	X	X	X	X	X	X	X	X	X		
Lower Leg Functional Assessments ¹³	TA & BB	TA & BB	TA		TA	TA	TA	TA	TA	TA	TA	TA	TA	TA & BB Day 190		TA	TA	TA & BB	
Upper Arm Functional Assessments ¹⁴	BB & TA	BB & TA	BB		BB	BB	BB	BB	BB	BB	BB	BB	BB	BB & TA Day 190		BB	BB	BB & TA	
FSHD-Health Index	X	X	X		X	X	X	X	X	X	X	X	X	X		X	X	X	
Monitoring of concomitant medications	X	X	X	X	X	X	X	X	X	X	X	X	X	X	X	X	X	X	
Monitoring of adverse events			X	X	X	X	X	X	X	X	X	X	X	X	X	X	X	X	
Randomization ¹⁵			X																
Study drug administration ¹⁶			X			X	X	X	X	X	X	X	X	X	X	X			
MMT assessment (MRC)	X													X			X	X	

¹ Study procedures must be done prior to administration of study drug. Reference the Study Manual for the order of study procedures. Laboratory samples and functional/strength assessments may be collected up to 24 hours prior to administration of study drug. Time of study drug administration is the time of the first injection. The Day 1 visit is timed relative to the Screening Day -28 to Day -21 visit. The Day -7 visit is timed relative to the scheduled Day 1 visit.

² All visit day windows should be considered relative to the date of the previous dose of study drug. Actual visit days may be different than planned (e.g., Day 8, Day 22) due to windows on visits and potential dosing delays.

³ Pregnancy test for women of childbearing potential to be performed and negative result confirmed before dosing.

⁴ Genetic testing for FSHD1/FSHD2 to be performed at screening if patient has not already had testing performed or previous results cannot be used to determine eligibility. Genetic testing for FSHD1/FSHD2 to be performed during the study if first degree relative is used for study eligibility but patient has not had testing previously performed or if patient's genetic documentation is inadequate with respect to FSHD1 D4Z4 fragment size or repeat number

⁵ Full physical examination includes skin, head, eyes, ears, nose, throat and neck, lymph nodes, cardiovascular, respiratory, gastrointestinal, musculoskeletal, and neurological

⁶ Limited physical examination includes skin, cardiovascular, respiratory, musculoskeletal and neurological assessments

⁷ Injection site examination including but not limited to evaluating erythema, pain, bruising, bleeding, and other signs of discomfort or skin reaction to be completed at least 30 minutes after injection.

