**4.1.4. Definitions of Baseline****Part 1 and Part 2 (Double-blind phase)**

For MRI, PD, and safety data, baseline is defined as the last non-missing assessment prior to the first dose of study drug administration. Theoretically, this is the Day 1 pre-dose assessment. For patients that are randomized (applicable to patients participating in Part 2) but do not receive any study drug administration, the date of randomization will be the baseline reference.

For motor function data (lower leg and upper arm functional assessments), strength (QMT by handheld device), gait, and FSHD-HI data whose pre-treatment assessments are performed up to three times prior to the first dose, the baseline is defined as the average of the non-missing values. Theoretically, this would be at the Screening Day -28, Screening Day -7, and Day 1 visits. The first dose date will serve as the reference from which the non-missing pre-treatment values would be identified. For patients that are randomized (applicable to patients participating in Part 2) but do not receive any study drug administration, the date of randomization will be the baseline reference. The last non-missing assessment prior to the first dose of study drug administration will also be determined for this data and will be available for sensitivity analyses for any analyses of changes from baseline as appropriate.

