Additional techniques for handling missing data may also be considered and evaluated.

- If a patient has a Day 190 assessment performed after having received the Day 190 dose (first dose in the open-label phase), then the Day 190 assessment for that patient will be included in statistical analyses of Day 190 data only if the difference between the Day 190 assessment and the Day 190 dose date is less than or equal to 7 days.
- Descriptive statistics for quantitative parameters will be provided using number of observations (N), mean, standard deviation (SD), standard error of the mean (SEM), median, minimum and maximum;
- Should it be necessary to convert duration in days to duration in months, the duration in days will be divided by 30.417 (365/12) to calculate duration in months.
- Descriptive statistics for qualitative parameters will be provided using frequencies (N) and percentages (%).
- If the result of a continuous variable contains nonnumeric values (e.g. ‘<X’ or ‘>X’), the imputed values used for the descriptive statistics will be determined by considering the following rules:
  - If the value is ‘<X’, the value used will be X/2;
  - If the value is ‘>X’, the value used will be X.
- Concerning the determination of absolute and percent change from baseline for data such as MRI and muscle strength where assessments are reported separately for the left and right sides and the average absolute and/or percent change from baseline is needed, the absolute and/or percent change is determined for the left and right sides separately and then averaged. The “average” represents the “average” absolute (or percent) change from baseline for the left and right sides. For MRI and muscle strength data, should a patient have an MRI and/or strength assessment on one side (i.e. right side) but not the other side at an individual timepoint, the value for the average absolute (or percent) change from baseline for that patient and timepoint will be the absolute (or percent) change from the side from which the MRI and/or strength assessment was obtained.

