## 4.2. Analysis Population

The analysis populations include the following:

- Full Analysis Set: Part 1 – All patients enrolled in the study receiving at least one dose of ACE-083. Part 2 – All patients randomized;
- Safety Set: All patients enrolled/randomized in the study who have received at least one dose of study drug (includes placebo);
- Per Protocol Set: All patients enrolled/randomized in the study who have received at least one dose of study drug (includes placebo) with no major protocol violations.
  - Major protocol violations include:

- Patients who discontinue the study prior to the Cycle 3 Day 43 visit; these patients are replaced per protocol
- Patients whose Day 1 MRI or Day 190 MRI was done 7 or more days following study drug administration
- Patients whose functional assessments (i.e. 10mW/R, mid-level PUL, 6MWT, 4-stair climb) at Day 1 or Day 190 were done 7 or more days following study drug administration
- Patients who did not receive the full study drug administration planned per protocol at all injection sites on any or both sides (right or left) for 2 or more consecutive visits for reasons other than dose reductions for the safety of the patient or feasibility concern (i.e., the site intended to administer the full dose but was unable).

Should the statistical analysis populations be identical (e.g., Full Analysis Set = Per Protocol Set), statistical analyses will not be duplicated or repeated.

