For BB patients, the above analyses will be repeated using the patient's "preferred" side used for the PUL test for patients.

The Per Protocol Set will be used for the primary analysis. The analyses described above will also be repeated for the Full Analysis Set.

Additional analyses may be performed as appropriate.

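### Day 190 values taken up to 7 days after the first open-label ACE-083 dose count as double-blind outcomes; the primary analysis should use pre-dose values only

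*SAP*

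**What the plan says.** Protocol 14.2.3.2 defines the primary endpoint as the "percent change in total muscle volume three weeks post last dose of the double-blind treatment period from baseline". SAP 4.7.2.2 places this at Day 190. At that visit all patients move to open-label ACE-083 (Protocol 7.1, SAP 3.2).

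The rules that bear on a late Day 190 assessment are these:

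- **Protocol Appendix 1, Table 6, footnotes 1 and 11.** "Study procedures must be done prior to administration of study drug", and MRI belongs in the 5 days before the scheduled dose. There is no post-dose allowance at Day 190.
- **SAP 4.1.5.** "If a patient has a Day 190 assessment performed after having received the Day 190 dose (first dose in the open-label phase"), the value is used in Day 190 analyses "only if the difference between the Day 190 assessment and the Day 190 dose date is less than or equal to 7 days".
- **SAP 4.2.** Major violations, which remove the patient from the Per Protocol Set, include "Patients whose Day 1 MRI or Day 190 MRI was done 7 or more days following study drug administration". A parallel bullet covers the 10-meter walk/run, mid-level PUL, 6-minute walk and 4-stair climb when these "at Day 1 or Day 190 were done 7 or more days following study drug administration". Strength (MVIC) and FSHD-HI are not listed.
- **SAP 4.7.2.2, total muscle volume.** "The Per Protocol Set will be used for the primary analysis", with a repeat on the Full Analysis Set.
- **SAP 4.1.4 and 4.1.5, Day 1.** For MRI, "baseline is defined as the last non-missing assessment prior to the first dose of study drug administration". A Day 1 value taken after dosing is not used as baseline.

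SAP Section 5, which lists departures from the protocol's statistical section, does not mention the 7-day rule.

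**The concern.** A placebo patient assessed after the Day 190 dose has received ACE-083, yet the value is analyzed as a placebo outcome. If the drug acts quickly, this narrows the treatment difference. If the injection itself enlarges the measured muscle for a few days, it adds noise.

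ACE-083 patients measured late are affected too, since their value follows a tenth active dose rather than nine. For MRI, strength and FSHD-HI the same Day 190 value is also the open-label baseline (SAP 4.1.4), so the problem carries into the extension comparison.

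The SAP is also uneven. It rejects post-dose values at Day 1 and accepts them at Day 190, without planning an analysis that would show whether this matters.

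**Working it through.** **1. Which late values reach the primary analysis.** SAP 4.1.5 decides whether a value is usable; SAP 4.2 decides whether the patient is in the primary set. Taken together:

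| Time of Day 190 assessment after the open-label dose | MRI and listed functional tests, Per Protocol Set | MVIC and FSHD-HI |
|---|---|---|
| Under 7 days | used | used |
| Exactly 7 days | patient excluded (value still used in the Full Analysis Set) | used |
| Over 7 days | patient excluded | value not used |

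The effective primary limit is thus under 7 days for muscle volume and the listed functional tests, and 7 days or less for MVIC and FSHD-HI.

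**2. The reference dose.** The 4.2 bullets do not say which administration they count from. An on-time Day 190 MRI falls 190 − 169 = 21 days after the Day 169 dose, or 16 days if done at the start of the 5-day window. Read literally, it would be a violation. The Day 190 dose is presumably meant.

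**3. The plan's power figure.** Inputs from Protocol 14.3: difference 10, SD 9, 12 per arm, two-sided alpha 0.10, t-test. The noncentrality is 10 / (9 × √(1/12 + 1/12)) = 2.72 with 22 degrees of freedom. Power is 83.9%, which agrees with the stated 83%.

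**4. Dilution.** Let k of 12 placebo patients be measured after the open-label dose, and let g be the share of the 10-point effect they have gained by then. The documents give neither, so both are assumed. Expected difference = 10 × (1 − (k/12) × g), with the SD held at 9 and the active arm unchanged. For k = 1: 10 × (1 − 0.10/12) = 9.92 and 10 × (1 − 0.50/12) = 9.58.

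| k of 12 | Difference, g = 0.10 to 0.50 | Power | Power if those k values are dropped without imputation |
|---|---|---|---|
| 0 | 10 | 83.9% | – |
| 1 | 9.92 to 9.58 | 83.4% to 81.1% | 82.4% |
| 2 | 9.83 to 9.17 | 82.8% to 78.0% | 80.5% |
| 3 | 9.75 to 8.75 | 82.3% to 74.6% | 78.3% |

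In each row the dropped-value power lies inside the range for keeping the values. Power therefore does not decide the question. The gain from dropping them is an estimate free of this dilution.

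**The case against.** The SAP rule handles deviations; it does not authorize late assessment, and the protocol's order of procedures stands. With about 12 patients per arm, a measured value a few days late may be thought better than one imputed from Days 43 and 106. This is a defensible pre-specified choice, and any dilution works against the sponsor if the drug is effective. All of that stands. It does not explain why no pre-dose-only analysis is planned, or why Day 1 is handled differently.

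Four stronger readings are tempting and are not supported:

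- **That the placebo control is broken.** Only patients measured out of order are affected, their number is unknown, and one or two move the estimate by less than a point across the assumed range.
- **That the two 7-day rules contradict each other.** They overlap at exactly 7 days, but one governs values and the other set membership, and both can be applied. This is untidy rather than unworkable.
- **That injected fluid gives a usable bound on the bias.** At the SAP 4.7.2.4 subgroup cut points, 50 mg/mL and a density of 1.06, injected volume is 3.5 × 1.06/50 = 7.4% (TA) and 2.9 × 1.06/50 = 6.1% (BB) of contractile volume. Patients above the cut points have larger shares, so this is no upper bound. Both arms receive the same injection at Day 190, so the fluid effect largely cancels if late timing is similar across arms.
- **That a Day 1 MRI done 1 to 6 days after dosing exposes a further rule conflict.** SAP 4.1.5 allows an unscheduled pre-dose scan as baseline, and SAP 4.7.2.2 plans imputation of baseline muscle volume when there is none.

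**Conclusion.** The point holds as a modest one. The SAP admits post-dose Day 190 values into the double-blind comparison, including the primary muscle volume analysis when the delay is under 7 days. This departs from the protocol's pre-dose schedule and from the SAP's own treatment of Day 1.

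The likely bias is small: about 0.1 to 0.4 points off a 10-point difference for one of 12 placebo patients, and 0.2 to 0.8 for two, toward no difference if the drug works. These figures rest on an assumed 10% to 50% of the effect appearing within the window, on late cases in the placebo arm only, and on an unchanged SD. The documents give no count of late assessments, so the actual size cannot be stated. Correcting the rule is a cheap improvement; nothing here suggests that the trial's conclusion depends on it.

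**What to change.** In SAP 4.1.5, restrict the primary analysis to Day 190 values obtained before the first open-label dose. Set later values to missing and let the planned multiple imputation handle them. Keep values within the 7-day window as a sensitivity analysis.

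In SAP 4.2, name the dose from which the delay is counted, and use one cut-off in 4.1.5 and 4.2 so that exactly 7 days is treated the same way in both. Do not turn every post-dose assessment into a Per Protocol violation. That would remove whole patients from the primary set instead of imputing single values, and a late walk test could then cost a valid pre-dose MRI.

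The cost is SAP wording and a few measured values replaced by imputed ones. Losing one of 12 placebo values with no imputation gives 82.4% power against 83.9%. Imputation may recover part of that; late values in the ACE-083 arm, also set to missing, would add to the loss.
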